4.2 Target of Estimation

The estimand (target of estimation) for Protocol AK002-016 is:

In subjects with EG and/or EoD, what is between group (AK002 vs. Placebo) difference in the proportion of tissue eosinophil responders at Week 24, and group difference in TSS change from baseline to Weeks 23–24 as measured by the patient-reported outcome (PRO) questionnaire.

The sections below describe the attributes of the estimand consistent with the ICH E9 (R1) Addendum ([FDA, 2021](#)).

4.2.1 Population Targeted by the Scientific Question

The population targeted by the scientific question is defined by the inclusion and exclusion criteria as part of the study protocol. Subjects must have a histological diagnosis of EG and/or EoD, as well as moderately to severely active symptomatic disease.

A key aspect of eligibility is that subjects must complete at least 4 daily PRO questionnaires per week for a minimum of 3 weeks during the screening period. In addition, subjects must have a weekly average score of abdominal pain, nausea, or diarrhea ≥ 3 on the PRO questionnaire (score from 0–10) for at least 2 weeks of screening and a weekly average TSS of ≥ 10 for at least 2 weeks of screening.

4.2.2 Variables of Interest (or Endpoint) to be Obtained for Each Subject that is Required to Address the Scientific Question

The co-primary endpoints to be obtained for each subject in this study to address the scientific question are [tissue eosinophil responders](#) (as defined in Table 2) at Week 24 and change in TSS from baseline to Weeks 23–24 as measured by the PRO questionnaire.

4.2.3 Treatment

AK002 or placebo administered to subjects on Days 1, 29, 57, 85, 113, and 141.

4.2.4 Intercurrent Events

The events below are considered intercurrent events (ICE) confounding with the efficacy outcomes.

- Premature discontinuation from the study
- Use of prohibited/restricted medication

Further clarification and handling of ICE including prohibited/rescue medications is detailed in [Appendix 2](#).

4.2.5 Strategy for Handling Intercurrent Events

For the analysis of the study product estimand, tissue eosinophil values and TSS will be counted as non-responders for binary variables and set to missing for continuous outcomes from the point when an ICE occurs. An appropriate method for handling missing data through statistical modeling (e.g., multiple imputation [MI]) will be used (Sections [5.4.1](#), [5.4.2](#), and [6.11](#)). The estimand will provide an answer to the question that is crucial to individual subjects:

“If I take this study drug as part of my treatment regimen, without adding any further medications that may impact the underlying disease or exit the study prematurely, what improvements in histology and PRO symptoms might be anticipated after 24 weeks?”

4.2.6 Summary Measure of the Estimand

- Percent (and 95% CI) of subjects having tissue eosinophil response at Week 24 in the AK002 and Placebo treatment groups and the absolute difference (and 95% CI) in the percent response between treatments.
- Least squares mean (LSM) (and standard error [SE]) of change from baseline to the average of Weeks 23–24 TSS and the between treatment difference in the AK002 and placebo treatment groups LSM.

5. Statistical Methods

5.1 General Methodology

All statistical analyses will be conducted using SAS v9.4 or later version on the Microsoft Windows Operating System.

All CRF data (raw data) will be converted into SDTM (Study Data Tabulation Model) datasets, which will be used to create ADaM (Analysis Data Model) data sets. The creation of the SDTM and ADaM data sets will follow the CDISC (Clinical Data Interchange Standards Consortium) standards and the FDA Study Data Technical Conformance Guide. All analysis tables and listings will be created from the ADaM data sets.

Continuous data will be summarized using “n” (number of subjects with non-missing observations), mean, median, standard deviation (SD), minimum value, and maximum value. Categorical data will be summarized using the frequency count and percentage (n, %) of subjects in each category. Number of subjects with non-missing values or number of subjects with missing values (e.g., Not Done) will be presented, where appropriate. Subjects with missing values will not contribute to the denominator for percentage calculations, unless specified otherwise. Counts of 0 in any category will be presented without percentage. All summaries will be presented for individual treatment groups. In addition, for summary of disposition and subject baseline characteristics, the presentation will include both treatment groups combined.

The precision rules for the presentation of summary statistics will be:

- Sample size (n, N) and number of missing responses (if displayed): Integer
- Mean, confidence interval, and median: Same number of decimal places as reported/collected
- Standard deviation: Same number of decimal places as reported/collected
- Percentiles, minimum, maximum: Same number of decimal places as reported/collected
- Odds Ratio: 2 decimal places
- Percentage: 1 decimal place generally, or 2 decimal places for <0.1%, or no decimal places for 0% and $\geq 100\%$
- P-value: 4 decimal places
- WBC: 2 decimal places as $0.01 \times 10^9/L$
- Height/Weight/BMI: 1 decimal place

The data summaries will be accompanied by individual subject data listings. All data available from questionnaires, eCRF, and external transfer (labs) will be listed and will include relevant subject information, e.g., treatment group and study day. The listings will be sorted in the order of treatment group, subject ID, assessment name and date/time.

Dates will be presented in the ISO-8601 format YYYY-MM-DD. Times will be displayed in 24-hour clock format. Numbering for tables, figures and listings will follow ICH E3 Guideline ([ICH, 1996](#)).

Alternative methods of analysis of the data may be considered prior to database lock should some of the assumptions underlying the proposed analyses not be met. Reason for departure from the planned methods will be documented as an amendment to the SAP or in the CSR.

5.2 Visit Window and Unscheduled Assessments

Data collected for study assessments provide information on the status of the subject at a given time point. These may provide biased results if the assessment is performed early or late.

Therefore, assessments will be slotted into analysis windows to allow summaries to be performed for subjects with similar study drug exposure. The analysis window is constructed by the medians of 2 target study days of the adjacent planned visits.

Table 3 Analysis Window Rules for CCI

Visit Description	Window
Baseline	On or Prior to Day 1 Predose
Day 1	Predose on infusion Day 1
Day 29	Day 1 Postdose to Day 42
Day 57	Day 43 to Day 70
Day 85	Day 71 to Day 98
Day 113	Day 99 to Day 126
Day 141	Day 127 to Day 158
Day 176	Day 159 to Day 186
Day 197	Day 187 to End of Study

Table 4 Analysis Window Rules for Vital Sign and Laboratory Tests

Visit Description	Window
Baseline	On or Prior to Day 1 Predose
Day 1	Day 1 Postdose
Day 15	Day 2 to Day 22
Day 29	Day 23 to Day 42
Day 57	Day 43 to Day 70
Day 85	Day 71 to Day 98
Day 113	Day 99 to Day 126
Day 141	Day 127 to Day 158
Day 176	Day 159 to 186
Day 197	Day 187 to End of Study

Table 5 Analysis Window Rules for PK Concentration and ADA

Visit Description	Window
Baseline	On or Prior to Day 1 Predose
Day 8	Day 1 Postdose to Day 11
Day 15	Day 12 to Day 22
Day 29	Day 23 to Day 42
Day 57	Day 43 to Day 70
Day 85	Day 71 to Day 98
Day 113	Day 99 to Day 126
Day 141	Day 127 to Day 154
Day 169	Day 155 to Day 172
Day 176	Day 173 to Day 186
Day 197	Day 187 to Day 210
Day 225	Day 211 to End of Study

Table 6 Analysis Window Rules for Blood Histamine and Urinalysis

Visit Description	Window
Baseline	On or Prior to Day 1 Predose
Day 1	Predose on Day 1
Day 29	Day 1 Postdose to Day 42
Day 57	Day 43 to Day 70
Day 85	Day 71 to Day 98
Day 113	Day 99 to Day 126
Day 141	Day 127 to Day 158
Day 176	Day 159 to Day 186
Day 197	Day 187 to End of Study

In the event of multiple values from unscheduled or early termination assessments within a single analysis window, the value closest to the scheduled visit target study day will be used for analyses. If 2 values tie as closest to the time point (for example, 1 value is before and the other value is after the time point), then the later value will be selected. Data collected at all visits will be included in the data listings with visit presented as reported by the site.

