11.2.5 Complete Blood Count with Differential

Blood will be obtained for complete blood count (CBC) with differential at the screening visit, as well as predose and 1 hour (± 15 minutes) postdose on Days 1, 29, 57, 85, 113, and 141 and on Days 8, 15, 169, 176, 197, and 225 or 28, 35, 56, and 84 (± 3) days after last dose of study drug if ET. The blood sample will be processed and shipped in accordance with laboratory manual and lab kit instructions. A central laboratory will analyze the blood sample and provide results for CBC with differential including hemoglobin, hematocrit, platelet count, red blood cell count, white blood cell count, and absolute differential count (neutrophils, lymphocytes, monocytes, eosinophils, and basophils).

The blood differential test results (neutrophils, eosinophils, basophils, monocytes, and lymphocytes) will be blinded from the Investigator and Sponsor from postdose Day 1 through Day 225 or ET and until database lock has occurred. As described in the Investigator's Brochure, these are part of the expected effects of AK002 and could potentially serve to introduce bias in blinded members of the study. The Safety Monitor will have real-time access to these laboratory results and will review and escalate any concerns/issues to the Medical Monitor and/or the site as appropriate. An unscheduled CBC with differential may be collected if requested by the Safety Monitor. All panic alerts for blinded values will be sent to the Safety Monitor and evaluated in real time.

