- 2) At screening, height (in cm) and weight (in kg) will be recorded. Body weight will also be measured on Days 1, 29, 57, 85, 113, 141 and on follow-up Days 176, 197, and 225 or 28, 56, and 84 days after last dose if ET. Current body weight or body weight from 1 day prior will be used to calculate the amount of AK002/placebo to be mixed with NaCl for the appropriate dose to be administered on each infusion day.
- 3) Vital signs will be measured at screening, Days 176, 197, and 225 or 28, 56, and 84 days after last dose if ET and on all dosing days: within 30 minutes predose, 15 minutes (± 5 minutes) after the start of study drug infusion, within 15 minutes following the end of infusion and just prior to discharge. Additional vital signs measurements may be collected at the Investigator's discretion if an IRR occurs. Vital signs including systolic and diastolic blood pressure, pulse, body temperature, and respiratory rate will be measured after the patient has been at rest for ≥ 5 minutes and before any blood draws have been obtained (unless collected for an IRR).
- 4) A 10-lead or 12-lead ECG will be obtained at screening before any blood is drawn and after the patient has been in the appropriate position for ≥ 5 minutes.
- 5) A complete physical examination will be performed by either the Investigator or designee and include the following body system or organ assessments: skin; head, eyes, ears, nose and throat; thyroid; lungs; cardiovascular; abdomen; extremities; lymph nodes; and a brief neurological examination.
- 6) A symptom-directed PE (including assessment of possible infusion site reactions) will be performed by the Investigator or designee, as needed if any symptoms are reported.
- 7) A baseline diet assessment (Protocol Appendix 3) will be performed using standardized questions. Eating patterns, food avoidance behaviors, and confirmed allergies will be captured.
- 8) A baseline diet compliance check will be performed at every study visit, except as noted above, and any variances from the baseline diet documented. Patients should maintain the baseline diet throughout the study.
- 9) Fecal collection kits for Ova and Parasite test will be provided to patients at screening. Collection kits should be returned to the clinical site within 1 day of collection. Negative results must be available prior to randomization.

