- 19) Premedication with 60 mg oral prednisone or approved alternative is required 12–24 hours prior to first infusion. Premedication may be administered prior to subsequent infusions at the Investigator's discretion, but only with written Medical Monitor approval.
- 20) Study drug will be administered as a single peripheral IV infusion over at least 4 hours for Dose 1 and at least 3 hours for Dose 2. Doses 3–6 should occur over at least 2 hours, depending on prior infusion tolerability. Please refer to the Pharmacy Manual.
- 21) Blood for CBC with differential, including absolute blood eosinophil count, will be obtained just prior to each infusion, 1 hour (± 15 minutes) after the end of each infusion as well as during the screening period, and on Days (± 3) 8, 15, 169, 176, 197, and 225 or 35, 56, and 84 (± 3) days after last dose if ET. All differential blood counts from Day 1 (post-dose) through the end of the patient's participation will be blinded to the Sponsor and the site. An unscheduled CBC may be collected at the request of the Safety Monitor.
- 22) Blood for chemistry will be obtained predose on dosing Days 1, 29, 57, 85, 113, and 141, as well as on Days 8, 15, 169, 176, 197, and 225 or 28 (± 3), 35 (± 3), 56 (± 3), and 84 (± 3) days after last dose of study drug if ET.
- 23) Blood for PK will be obtained predose on dosing Days 29, 57, 85, 113, and 141, as well as during screening and on Days 8, 15, 169, 176, 197, and 225 or 28 (± 3), 35 (± 3), 56 (± 3), and 84 (± 3) days after last dose of study drug if ET.
- 24) Blood for ADA will be collected predose on dosing Days 29, 57, 85, 113, and 141, as well as during screening and on Days 8, 15, 169, 176, 197, and 225 or 28 (± 3), 35 (± 3), 56 (± 3), and 84 (± 3) days after last dose of study drug if ET. ADA sample will also be collected any time an immunogenicity-related AE occurs.
- 25) Urine for standard urinalysis will be obtained predose on dosing Days 1, 29, 57, 85, 113, and 141 as well as during the screening period and on Day 176 and Day 197 or 35 (± 3) days and 56 (± 3) days after last dose of study drug if ET.
- 26) A small amount of urine collected for urinalysis will be used for dipstick pregnancy test on all infusion days and on Day 176 and 197 or 35 and 56 (± 3) days after last dose of study drug, for all patients of childbearing potential. Test kits will be supplied by the central laboratory. Tests will be completed on site and evaluated prior to each infusion.

Table 1 Notes cont.

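### SAP Table 4 gives no window to the scheduled Day 8, 169 and 225 CBC and chemistry draws or the Day 225 vital signs, so by-visit safety tables may mislabel or drop them

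*SAP*

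**What the plan says.** SAP 5.2 slots assessments into windows so that patients with similar drug exposure are summarised together, and gives the construction rule: "The analysis window is constructed by the medians of 2 target study days of the adjacent planned visits". When a window holds more than one value, the closest to the target day is used and ties go to the later value. That instruction is worded for "multiple values from unscheduled or early termination assessments within a single analysis window". Listings keep the visit as the site reported it.

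The schedules are these:

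- **CBC** (Protocol 11.2.5): screening, pre-dose and 1 hour "postdose on Days 1, 29, 57, 85, 113, and 141 and on Days 8, 15, 169, 176, 197, and 225".
- **Chemistry** (SAP Table 1, note 22): pre-dose on dosing days, "as well as on Days 8, 15, 169, 176, 197, and 225".
- **Vital signs** (SAP Table 1, note 3): "Vital signs will be measured at screening, Days 176, 197, and 225", with early-termination equivalents ending at "84 days after last dose if ET and on all dosing days". None are scheduled on Days 8, 15 or 169.

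After the Day 1 post-dose row, Table 4 has rows for Days 15 (2–22), 29, 57, 85, 113, 141 (127–158), 176 (159–186) and 197 (187 to end of study). Table 5, for PK and ADA, also has rows for Day 8 (to Day 11), Day 169 ("Day 155 to Day 172") and Day 225 (from Day 211). SAP 6.15.2 and 6.15.3 apply the windows to the laboratory and vital-sign summaries.

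**The concern.** The other window tables follow the schedule of what they cover. Tables 3 and 6 cover assessments not planned on Days 8 or 15, and their Day 29 row runs from "Day 1 Postdose to Day 42". Table 5 covers assessments planned on Days 8, 169 and 225 and has a row for each. From Day 29 onward Table 4 is identical to Tables 3 and 6, which suggests that it was built on their schedule and not on the CBC and chemistry schedule. That is an inference; the SAP gives no reason.

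At stake are the by-visit change and shift tables for haematology and chemistry and the vital-sign summary (SAP Appendix 3, Tables 14.3.2.1 to 14.3.2.4 and 14.3.3). Protocol 15.7.3 and 15.7.4 call for these summaries at each visit. The provisional lock in SAP 5.6 is for an analysis of data through Day 169, yet the Day 169 laboratory values have no row and fall in one labelled Day 176. The Day 197 row would hold values taken 56 and 84 days after the last dose. Protocol 7.4 (exclusion 18) equates 5 half-lives with 4 months. Taking 4 months as about 120 days, one half-life is about 24 days, so the 28-day gap is more than one half-life.

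**Working it through.** **1. Does the midpoint rule reproduce the tables?** The cut is (a + b)/2 for adjacent planned days a and b.

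| Adjacent days | Midpoint | Table 5 boundary | Table 4 boundary |
|---|---|---|---|
| 8 / 15 | 11.5 | 11/12 | none |
| 15 / 29 | 22 | 22/23 | 22/23 |
| 141 / 169 | 155 | 154/155 | none |
| 169 / 176 | 172.5 | 172/173 | none |
| 141 / 176 (Day 169 left out) | 158.5 | not used | 158/159 |
| 176 / 197 | 186.5 | 186/187 | 186/187 |
| 197 / 225 | 211 | 210/211 | none |

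The rule reproduces Table 5. Table 4's 158/159 cut arises only if Day 169 is left out. That is right for vital signs, which are not taken on Day 169, and wrong for CBC and chemistry.

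**2. Where do the values go under Table 4?** Every in-tolerance day was mapped to its window.

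- Day 8: Days 6–10 (or 5–11 under the ±3 in the CBC note) all fall in the Day 15 row, nominally |8 − 15| = 7 days off.
- Day 169: Days 166–172 all fall in the Day 176 row, |169 − 176| = 7 days off.
- Day 225: Days 222–228 all fall in the Day 197 row, |225 − 197| = 28 days off.

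**3. What if the closest-value rule were extended to scheduled values?** Over all pairs of in-tolerance days, the value from the visit without a row is chosen in 0 of 25 pairs (Day 8 against 15, ±2), 0 of 49 (Day 169 against 176) and 0 of 49 (Day 225 against 197), with no ties. It would be left out whenever the named visit's value exists.

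**4. How many laboratory days have no row?** The post-Day-1 days are 8, 15, 29, 57, 85, 113, 141, 169, 176, 197 and 225.

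| Completing patient | Laboratory days | Without a row | Share |
|---|---|---|---|
| Enters extension before Day 197 | 9 | 2 (Days 8, 169) | 22.2% |
| Enters between Days 197 and 225 | 10 | 2 (Days 8, 169) | 20.0% |
| Full follow-up | 11 | 3 (Days 8, 169, 225) | 27.3% |

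Assume 160 completers, with a, b and c patients in these three groups. The trial-level share is (2a + 2b + 3c)/(9a + 10b + 11c). Its extremes are 320/1600 = 20.0% (all in the second group) and 480/1760 = 27.3% (all in the third). As an illustration only, with 144 patients (90%) entering before Day 197:

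- other 16 with full follow-up: (288 + 48)/(1296 + 176) = 336/1472 = 22.8%;
- other 16 entering between Days 197 and 225: (288 + 32)/(1296 + 160) = 320/1456 = 22.0%.

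**5. Vital signs.** The post-Day-1 visits number 6, 7 and 8 in the three groups. Only Day 225 lacks a row, so 0 of 6, 0 of 7 and 1 of 8 are affected.

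**6. Rows shared by two scheduled visits.** For laboratory tests this is 3 of 8 rows with full follow-up and 2 of 7 populated rows for entrants before Day 197. For vital signs it is one row (Day 197), and only with full follow-up.

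**The case against.** The strongest reply is that the windows group by exposure, and the pooled visits are mostly alike in that respect: Days 8 and 15 both follow the first dose, and Days 169 and 176 both follow the last. Safety rests mainly on adverse events (SAP 6.15.1), no formal inference is made on safety parameters (Protocol 15), clinically significant laboratory values are recorded as adverse events (Protocol 11.4), and the Safety Monitor sees differentials in real time (Protocol 11.2.5). All of this stands and keeps the point minor. It does not explain why Table 4 departs from the stated rule, and it does not cover Days 197 and 225.

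Three stronger readings are tempting, but the documents do not support them.

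- A reader might infer that the Day 8, 169 and 225 values will certainly appear under another visit's label. The SAP does not settle this, because its selection rule does not reach two scheduled values in one window. They may be mislabelled or dropped, so the counts above are days without a row, not days mislabelled.
- A reader might infer that the vital-sign Day 15 row is an error to delete. No vital signs are scheduled then, but an unused row does no harm. If it were removed and the Day 29 row began at Day 2, an unscheduled or early-termination reading on Days 2–14 could be up to 27 days off label, against at most 13 now.
- A reader might infer that the choice between pre-dose and 1-hour CBC values is wholly unspecified. SAP 6.15.2 summarises by visit without time point, but redacted sections may deal with some counts. The Protocol synopsis describes a redacted measure taken before and 1 hour after each infusion.

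**Conclusion.** The point holds. Table 4 breaks the SAP's own rule for CBC and chemistry at Days 8, 169 and 225 and for vital signs at Day 225, and following it as written gives by-visit tables that mislabel or omit scheduled values. Between 20% and 27% of post-Day-1 laboratory days in completing patients have no row of their own. Where the trial falls in that range depends on when patients enter the extension, which the documents do not give; the Phase 2 uptake of more than 90% says nothing about timing. The counts assume that completers attend every scheduled visit.

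Severity is minor. Only descriptive safety tables are affected, including those for the analysis through Day 169. Neither co-primary analysis uses these windows, and the listings stay correct. The CBC time-point question is secondary and subject to the redactions.

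**What to change.** Split Table 4 in two.

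- **CBC and chemistry:** keep Baseline and Day 1 Postdose, then Day 8 (2–11), Day 15 (12–22), Days 29 to 113 unchanged, Day 141 (127–154), Day 169 (155–172), Day 176 (173–186), Day 197 (187–210), Day 225 (211 to end of study). These are the Table 5 cuts, except that Day 8 starts at Day 2 because Day 1 post-dose has its own row. Every in-tolerance day then falls in its own row.
- **Vital signs:** end the Day 197 row at Day 210 and add Day 225 (211 to end of study). Leave the other rows, including Day 15, as they are.
- **Selection rule:** state that the closest-value and tie rules apply to any multiple values in a window, scheduled or not, within a time point. The last condition matters: pre-dose and 1-hour CBC values on one day tie on distance, and the tie rule would then take the 1-hour value, although transient post-infusion lymphopenia is already known (Protocol synopsis, Clinical Background).
- **Secondary:** summarise haematology by visit and time point (pre-dose, 1 hour post-dose), as SAP 6.15.3 does for vital signs, unless a redacted section already does so.

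The cost is one table split, three more laboratory rows, one more vital-sign row, a sentence or two, and a time-point split in the haematology tables. No new data are needed. The change is best made by SAP amendment before the provisional lock.

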11.4 Clinical Laboratory Measurements

Blood and urine samples for clinical safety laboratory tests will be collected at the time points described below and in Table 1. Investigators may have additional laboratory tests performed for the purpose of planning treatment administration or following AE or abnormal lab values.

The site will process and ship blood and urine samples per central laboratory instructions. A central laboratory or designee will analyze blood and urine samples and provide results for the following clinical safety laboratory tests.

Clinical laboratory testing may be performed locally if the site thinks the central laboratory may not be able to provide results in a timely fashion due to staff reductions, shipping issues, or other factors associated with the COVID-19 pandemic. The site will strive to use the central laboratory whenever possible.

For any laboratory test value outside the reference range, the Investigator will determine clinical significance: Not Clinically Significant (NCS) or Clinically Significant (CS). An abnormal lab value should be deemed CS if any of the following conditions are met:

- The abnormality suggests a disease and/or organ toxicity that is new or has worsened from baseline.
- The abnormality is of a degree that requires additional active management, e.g., change of study drug dose, discontinuation of the study drug, close observation, more frequent follow-up assessments, or further diagnostic investigation.

Therefore, a clinically significant lab value is one that indicates a new disease process, an exacerbation or worsening of an existing condition, or requires further action to be taken.

For any laboratory test value outside the reference range that the Investigator considers clinically significant, the Investigator will:

- Repeat the test to verify the out-of-range value.
- Follow the out-of-range value to a satisfactory clinical resolution.
- Record as an AE any laboratory test value after start of study drug that:
 - The Investigator considers clinically significant
 - Requires a patient to be discontinued from the study
 - Requires a patient to receive treatment

Blood will be obtained for CBC with differential as described in Section 11.2.5.

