13.10 Study Withdrawal Criteria

Participation of a patient will be discontinued in the event that:

- Occurrence of an exclusion criterion, which is clinically relevant and affects the patient's safety, if discontinuation is considered necessary by the Investigator and/or Sponsor.
- Rebounding of eosinophil counts to $>1500/\mu\text{L}$ in patients who entered the study with eosinophil levels $>1500/\mu\text{L}$, and whose eosinophil counts were initially suppressed after study drug will be withdrawn from the study at the instruction of the Safety Monitor.
- Serum transaminases (ALT and/or AST) $>3 \times \text{ULN}$ and total bilirubin $>2 \times \text{ULN}$ (confirmed by subsequent repeat) without an alternative explanation.
- Elevation of ALT or AST $>3 \times \text{ULN}$ (confirmed by repeat) with the appearance or worsening of symptoms felt by the Investigator to be potentially related to hepatic inflammation, such as fatigue, nausea, vomiting, right upper quadrant pain or tenderness, fever, rash.

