6.15.2 Laboratory Test

Laboratory data will be summarized by presenting summary statistics of raw data and change from baseline values (means, medians, standard deviations, ranges). For quantitative laboratory parameters, both actual values and change from baseline values will be summarized at each visit.

Shift tables will be presented, in which, lab test results at baseline and post-baseline visit will be classified into below ($<\text{LLN}$), within ($\geq\text{LLN}$ and $\leq\text{ULN}$), and above ($>\text{ULN}$) normal ranges.

Subject incidences (n and %) will be presented for the shift from baseline to the post-baseline visits.

Note that the analysis window will be applied for the visits.

A complete laboratory data listing, including hematology, biochemistry, and urinalysis will be provided for all subjects.

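### Laboratory tables keep one value per window and three normal-range classes, so worst values and patient counts at the protocol's liver thresholds are not tabulated as laboratory results

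*SAP*

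**What the plan says.** **Selecting the value.** SAP 5.2 opens its rule with "In the event of multiple values from unscheduled or early termination assessments within a single analysis window" and continues that "the value closest to the scheduled visit target study day will be used for analyses". If two values are equally close, "then the later value will be selected". What is not selected is still listed: "Data collected at all visits will be included in the data listings with visit presented as reported by the site".

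**Windows.** SAP 5.2 states: "The analysis window is constructed by the medians of 2 target study days of the adjacent planned visits". Table 4 (vital signs and laboratory tests) has post-baseline targets at Days 1 (postdose), 15, 29, 57, 85, 113, 141, 176 and 197. Table 5 (PK and ADA) also has Days 8, 169 and 225.

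**Tables.** SAP 6.15.2 summarises laboratory data by visit (means, medians, SDs, ranges) with the windows applied. For shifts, "lab test results at baseline and post-baseline visit will be classified into below", within or above the normal range. SAP Appendix 3 lists change-from-baseline tables by visit for hematology, chemistry and urinalysis, and shift tables by visit for hematology and chemistry.

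**Repeats.** For a clinically significant out-of-range value, Protocol 11.4 tells the investigator: "Repeat the test to verify the out-of-range value". Protocol 13.10 has two liver criteria. One is ALT and/or AST >3 x ULN together with total bilirubin >2 x ULN, "confirmed by subsequent repeat) without an alternative explanation". The other is ALT or AST >3 x ULN, confirmed by repeat, with new or worsening symptoms.

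**The concern.** The protocol builds repeat sampling into the handling of abnormal results, and the SAP then lets one value per window into the tables on calendar distance alone. A repeat can take the place of the abnormal value that prompted it, and a peak found away from the target day can drop out.

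The shift classes add a second loss. A value of 1.1 x ULN and one of 8 x ULN are both simply above normal, and each visit is shown separately. A reader of the tables could not learn how many patients in each arm ever exceeded 3 x ULN on ALT or AST, or in how many bilirubin exceeded 2 x ULN as well, although the protocol uses these limits for withdrawal. Comparative laboratory safety would have to be pieced together from listings.

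**Working it through.** **1. Reproducing the Table 4 windows.** Midpoints of adjacent Table 4 targets, with the stated window end in brackets:

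- (15+29)/2 = 22 [22]
- (29+57)/2 = 43 [42]
- (57+85)/2 = 71 [70]
- (85+113)/2 = 99 [98]
- (113+141)/2 = 127 [126]
- (141+176)/2 = 158.5 [158]
- (176+197)/2 = 186.5 [186]

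All agree within one day, but only with Days 8, 169 and 225 left out as targets. With Day 169 included, the Day 141 window would end near (141+169)/2 = 155; Table 5 has 154 and Table 4 has 158.

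**2. Scheduled draws that share a window.** Protocol 11.5 schedules post-baseline chemistry on Days 8, 15, 29, 57, 85, 113, 141, 169, 176, 197 and 225, which is 11 draws. CBC is also drawn on Days 8, 169 and 225 (Protocol 11.2.5). If nearest-to-target covers scheduled values and both draws are in their visit windows:

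- Day 8 (±2) against target 15: the Day 8 draw is at least 15 − 10 = 5 days away and the Day 15 draw at most 2. Day 15 wins in 25 of 25 combinations.
- Day 169 (±3) against target 176: at least 176 − 172 = 4 days against at most 3. Day 176 wins in 49 of 49.
- Day 225 (±3) against target 197: at least 222 − 197 = 25 days against at most 3. Day 197 wins in 49 of 49.

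So 3 of 11 chemistry draws never reach the by-visit tables when their neighbour is taken. On dosing Days 29 to 141, predose and 1-hour postdose CBC share a study day and a window. Counted in whole days they tie, and the later, postdose value is kept.

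**3. When a repeat replaces a scheduled value.** Let the scheduled draw be d days before target and the repeat g days after the draw. The repeat is |g − d| days from target and is selected when |g − d| ≤ d, that is g ≤ 2d. If the draw is on or after target, a later repeat is always further away and is never selected.

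For target Day 57, a Day 54 draw (d = 3) is replaced by a repeat on Day 58 (1 day from target against 3) or Day 60 (a tie, so the later). A Day 57 draw is kept against a Day 60 repeat.

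Over the seven visit days of a ±3 window:

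- g = 1–2 needs d ≥ 1: 3/7 = 43%
- g = 3–4 needs d ≥ 2: 2/7 = 29%
- g = 5–6 needs d = 3: 1/7 = 14%
- g ≥ 7: 0

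For Day 15 (±2) the shares are 2/5, 1/5 and 0. These are conditional on an abnormal scheduled value with a repeat at that lag, and they assume uniform visit days, which the documents do not state. Over a ±3 window the range is 0% if every draw is on or after target, up to 100% for lags of 1–6 days if every draw is three days early.

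**4. Off-target peaks.** An unscheduled sample on Day 64 lies in the Day 57 window (Days 43–70) but is 7 days from target. Any in-window scheduled draw is at most 3 days away, so the Day 64 value is listed only.

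**5. Table list.** None of the laboratory tables in SAP Appendix 3 is a worst-post-baseline, toxicity-grade or ULN-multiple table.

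**The case against.** A reader might infer that these values never reach a table. The documents do not support that. The values Protocol 11.4 requires to be repeated are also to be recorded as adverse events, and SAP 6.15.1 tabulates those by preferred term, maximum severity and discontinuation. Discontinuation of study drug for meeting Protocol 13.10 is an intercurrent event (SAP Appendix 2, item C.1.c), counted by category under SAP 6.11. A selected peak shows as the maximum in the by-visit ranges.

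These routes do not supply the missing count. The adverse event route rests on the investigator's judgement of significance (or on treatment or discontinuation) and counts preferred terms, not ULN multiples. Item C.1.c pools all 13.10 criteria, including eosinophil rebound, and applies only if study drug is stopped. A range gives one extreme value, not a number of patients, and does not link ALT with bilirubin in the same patient.

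Other parts of the case against stand:

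- The rule's opening words name unscheduled and early termination values. Whether a scheduled value competes is unclear, and replacement holds only on the reading that it does.
- A case meeting 13.10 has a confirming high repeat, so a swap leaves it above ULN. Displacement mainly affects unconfirmed peaks and the size of confirmed ones.
- The rule is blind to the result. An abnormal unscheduled sample nearer target can equally replace a normal early one.
- Protocol 15.7.3 promises by-visit summaries and normal-range shifts, no formal safety inference is planned, and all values are listed.

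**Conclusion.** The point holds as a gap in tabulation. It is worth fixing before database lock, and it does not touch the co-primary endpoints. That no planned laboratory table shows worst values or threshold counts follows directly from SAP 6.15.2 and Appendix 3 and needs no assumption. The loss of the Day 8, 169 and 225 draws (3 of 11) and the replacement by repeats both assume that SAP 5.2 covers scheduled values. If it does not, the SAP has no rule for choosing between two scheduled values, or a scheduled value and a repeat, in one window. Either reading needs repair.

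Three stronger conclusions are not supported. The 3/7 share does not mean that 43% of visits lose a value; it is illustrative and conditional as set out above. Systematic understatement of abnormality, or bias between arms, is possible but not shown. Bilirubin >2 x ULN alone, or ALT/AST >3 x ULN without symptoms or raised bilirubin, is not a 13.10 criterion.

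**What to change.** 1. In SAP 6.15.2 and Appendix 3, add a shift from baseline to worst post-baseline value using all samples, including unscheduled ones. Add a count by arm of patients ever above 3 x ULN on ALT or AST, with and without bilirubin above 2 x ULN. This tabulates limits the protocol already uses and changes no withdrawal rule.
2. In SAP 5.2, state that by-visit laboratory summaries use the scheduled sample when present and an unscheduled one only when it is missing. Give Days 8, 169 and 225 their own Table 4 windows, as in Table 5, so that no window holds two scheduled visits. Keep predose and postdose CBC as separate time points.

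The two parts belong together: a scheduled-first rule alone would keep every unscheduled peak out of the by-visit tables whenever a scheduled sample exists, and the worst-value table recovers those peaks. The cost is SAP wording and one or two extra tables from data already collected.
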